**Evaluation of Wear Experience with PRECISION7® For Astigmatism Contact
Lenses in Neophyte Lens Wearers**

NCT: NCT06751225

Document Date: 25-Nov-2024

Evaluation of Wear Experience with PRECISION7® For Astigmatism Contact Lenses in Neophyte Lens Wearers

[name], OD MS

The Ohio State University College of Optometry
Innovation in Vision and Eye care Research Group - iVERG
[name]
[name]
[contact]

Purpose

The purpose of this study is to explore the wear experience with PRECISION7® For Astigmatism lenses in adults who have not previously worn contact lenses.

Study Overview

This open-label study is of adults with astigmatism who have never worn contact lenses. Subjects will be fit into PRECISION7® For Astigmatism contact lenses and will wear lenses for approximately 3 weeks. Subjects will return for vision and lens fit assessments and will complete surveys about their wear experience.

Background

Soft daily wear contact lenses are used by an estimated 40.9 million adults in the United States.¹ Contact lenses which are worn for daily wear are considered minimal risk by the FDA, and risks to wearers are minimized by proper lens care and hygiene. The subjects in this study are adults with astigmatism that have never worn contact lenses who will be fit into PRECISION7® For Astigmatism, a 1-week replacement reusable contact lens.

Key Endpoints:

- Subjective assessment of P7 experience with CLDEQ-8, Visual Analog Scale survey of lens wear symptoms, and questionnaire about quality of life/preference of lens modality experiences.

Study Time Points:

After responding to recruitment material, potential participants will respond to pre-screening questions to determine initial eligibility. Those eligible will be scheduled for a screening visit and will complete the informed consent process. Manifest refraction, Best Corrected Visual acuity, and an evaluation of the participant's ocular health will occur. The OSDI questionnaire will also be complete to assess if the participant has dry eye. The fit of PRECISION7® For Astigmatism lenses will be analyzed and optimized before dispensing a pair of lenses for 1 week of wear (-3 days). The participant will be trained on insertion/removal and contact lens hygiene.

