Visit 2: PRECISION7® For Astigmatism follow up visit. Vision, lens fit and ocular health will be assessed. If lens fit and eye health are acceptable, PRECISION7® for Astigmatism Contact Lenses will be dispensed and a contact lens follow-up visit scheduled for 2 weeks (-3 days). If an additional study visit is required because the lens power or fit must be changed at this visit, new lenses will be dispensed/ordered and Visit 2 will be repeated after 1 week of wear with the optimized lenses. (Participants will be compensated for a repeat visit.)

Visit 3: The contact lens follow up visit will occur approximately 2 weeks (-3 days) following the initial fitting. Subjects will have visual acuity, an assessment of ocular health, and lens fit completed. Subjects will then complete surveys about their lens wear experience.

All surveys at visit 3 will be completed in REDCap.^{2,3}

Surveys will include:

CLDEQ-8

VAS survey of comfort/dryness/vision

0-100 scale:

Overall vision throughout the week

Overall vision while on digital device

Stability of vision at end of day

Stability of vision throughout the week

Overall comfort throughout the week

Overall comfort throughout the day

Overall comfort while on digital device

End of Study Wear Experience

Convenience of 1 week replacement lens

Would you purchase PRECISION7 for Astigmatism?

How easy is it to apply the lenses to your eye?

How easy is it to remove lenses?

Recruitment

Potential participants may see posters placed on bulletin boards locally, at The Ohio State University, or local eye care offices, student dorms, emails to students, faculty and staff at OSU, online or paper ads, or signs on the OSU buses. Facebook advertising through the CCTS will occur. A search of the electronic medical records of The Ohio State College of Optometry may be done to identify possible subjects who then may be contacted by email or phone with information about the study. Word of mouth referrals by study team members to OSU employees and friends may occur. Emails to alumni of the OSU College of Optometry may be sent for local doctors to notify eligible potential subjects about the study.

Inclusion:

1. Subjects must be new to contact lenses and have astigmatism of -0.75 or greater (within the parameters available for the P7fA lenses)
2. Subjects must have 20/20 or better best corrected visual acuity.

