Subjects who, after study team member coaching, are not able to provide analyzable data may be dismissed from the study. Analyzable data is, for example, that which is obtained for the entire measurement interval and provides a readable eye image. Data may not be analyzable if patient isn't able to stand or move freely to utilize the equipment, to name just two causes issues. These issues are usually revealed at the screening assessment visit. Subjects who cannot provide analyzable data will be dismissed for the study. Subjects who do not keep scheduled visits within the required time frame will be dismissed from the study. Study team members will make reasonable efforts to accommodate subjects' schedules.

Protocol Violations, Discontinuation

In the event that a member of the study team or a representative of sponsor becomes aware of a major protocol violation, the IRB shall be notified within 10 working days.

References

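### The late-visit dismissal rule rests on minus-only windows and two conflicting Visit 3 anchors, and it can lose survey endpoints that could still be collected

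*Combined protocol and SAP*

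**What the plan says.** **Late visits.** Subject Dismissal: "Subjects who do not keep scheduled visits within the required time frame will be dismissed from the study". No grace period or exception follows, only an undertaking to make reasonable scheduling efforts.

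**Windows.** Study Time Points describes "dispensing a pair of lenses for 1 week of wear (-3 days") before Visit 2. At Visit 2 it then provides for "a contact lens follow-up visit scheduled for 2 weeks (-3 days"). The Visit 3 paragraph repeats the two weeks and the minus 3 days but counts them from the initial fitting, with the word *approximately* in front. Study Overview gives total wear as about 3 weeks.

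**Endpoints.** Key Endpoints are questionnaires: CLDEQ-8, visual analogue scales, and a quality-of-life and preference questionnaire. Study Time Points lists the surveys of wear experience only at Visit 3, after the clinical checks.

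**Analyzable data.** Subject Dismissal first says: "Subjects who, after study team member coaching, are not able to provide analyzable data may be dismissed from the study". It then gives an illustration: "Analyzable data is, for example, that which is obtained for the entire measurement interval and provides a readable eye image". Later in the same paragraph it says: "Subjects who cannot provide analyzable data will be dismissed for the study".

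**Analysis.** Statistical Analysis plans descriptive statistics, with 60 screened so that 40 complete. No analysis set is defined.

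**The concern.** A rule that removes subjects must be applicable in the same way to everyone, and it should not cost the study its endpoints without need. This rule is weak on both counts. The time frame it depends on has no late side and, for Visit 3, two starting points. The endpoints come from a survey at the last visit, which a subject arriving a day late can still answer.

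What is at stake is mainly who is described. Subjects who struggle with the lenses or dislike them may be the ones who attend late. If they are removed, the reported comfort, vision and preference ratings describe those who got on well. A single-arm descriptive study has no comparator in which a similar loss might offset this.

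A smaller matter is the analyzable-data text. It offers a second ground for dismissal that corresponds to nothing in the listed visit procedures.

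**Working it through.** **The plan's own figure.** 60 screened for 40 completers implies a loss of 1 − 40/60 = 33.3% from screening to completion. The plan does not split this between screen failure, drop-out and dismissal. It can be neither derived nor shown to be wrong.

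**Windows** (day 0 = initial fitting, inputs from Study Time Points):

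- Visit 2: 7 − 3 = day 4, to day 7.
- Visit 3 counted from Visit 2: 14 − 3 = 11 to 14 days later. Earliest 4 + 11 = day 15, latest 7 + 14 = day 21. With Visit 2 on day 7, the range is days 18 to 21.
- Visit 3 counted from the initial fitting: 14 − 3 = day 11, to day 14.

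Days 15-21 and days 11-14 have no day in common, so a subject on time under one statement is outside the other. The roughly 3 weeks in Study Overview agree with 7 + 14 = 21 and not with 14. One repeat of Visit 2 after a further week, with lenses dispensed the same day, can move Visit 3 to 7 + 7 + 14 = day 28.

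**Where endpoint data are lost.**

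- Late Visit 2: dismissal comes before any survey of wear experience, so no endpoint data exist.
- Late Visit 3: the plan does not say whether the subject completes the surveys, or whether they are reported.

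**How many.** The documents give no lateness rate. As an illustration, assume each of the two follow-up visits is late with probability q, independently, and every late subject is dismissed. The dismissed share is 1 − (1 − q)².

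| q (assumed) | Dismissed | Completers if 40 are fitted | Fitted to reach 40 |
|---|---|---|---|
| 5% | 1 − 0.95² = 9.75% | 36.1 | 40/0.9025 = 44.3, so 45 |
| 10% | 1 − 0.90² = 19% | 32.4 | 40/0.81 = 49.4, so 50 |
| 20% | 1 − 0.80² = 36% | 25.6 | 40/0.64 = 62.5, so 63 |

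Only the last row needs more subjects than the 60 to be screened.

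**Precision.** The 95% half-width for a proportion of 0.5 is 1.96 × √(0.25/n): 15.5 percentage points at n = 40, 16.3 at 36, 17.3 at 32. For a mean, 1.96/√n gives 0.31, 0.33 and 0.35 SD.

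**Selection.** Let d be the share dismissed and D the gap in mean score between retained and dismissed subjects. The mean among all subjects is (1 − d) × retained mean + d × dismissed mean, so the retained mean exceeds it by d × D. With a higher score taken as better, and D assumed:

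- d = 10%: 0.10 × 10 = 1 point; 0.10 × 20 = 2 points.
- d = 20%: 0.20 × 10 = 2 points; 0.20 × 20 = 4 points.

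Fitting more subjects until 40 complete restores the precision but leaves this shift in place.

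**Analyzable-data text.** The listed procedures are refraction, acuity, ocular health, lens fit, OSDI at screening and the surveys. None is described as having a measurement interval or as producing an image. The paragraph also says first that such subjects *may*, and then that they *will*, be dismissed.

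**The case against.** Several points on the other side are fair.

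- **The windows may be deliberate and are softened.** The lens is a one-week replacement product, so a plus side could run past the replacement interval. One Visit 3 statement says *approximately*, and staff are to accommodate schedules. This stands as a possible reason for the minus-only form. But *approximately* sets no tolerance, scheduling effort does not say what happens once a visit is late, and neither resolves the two anchors. A reason concerning lens wear is also not a reason to forgo a survey.
- **Timing is not irrelevant to the endpoints.** Survey items ask about vision and comfort over the week. True, and a good reason to record the actual day; it does not make a late answer unusable.
- **The numerical harm is modest.** The lateness rate is assumed, and at 10% per visit 50 fitted subjects would still give 50 × 0.81 = 40.5 completers. For a descriptive pilot the loss of precision is minor. This stands.
- **Informative lateness is a conjecture.** It is plausible, but the documents neither support nor exclude it.

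A reader might infer that completed survey data are thrown away. The documents do not say so: they dismiss subjects, do not exclude data, and Data Management and Security keeps a disenrolled subject's paperwork. A reader might also infer that no imaging is done, or that the paragraph was carried over from another protocol. Imaging is only not listed, and carry-over cannot be shown. The readable image is given as an example, and the section says such problems usually appear at screening, so this text probably has little practical effect.

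**Conclusion.** The point holds in limited form. The late-visit rule is mandatory, its windows have no late side, and the two Visit 3 anchors give ranges that do not overlap, so the rule cannot be applied consistently as written. That much rests on the text and day arithmetic alone. It also follows from the text that dismissal at a late Visit 2 prevents endpoint collection, and that the plan is silent on surveys at a late Visit 3.

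The size rests on assumptions. If 20% of subjects are lost and would have scored 10 to 20 points lower, the 0-100 mean is raised by 2 to 4 points; if lateness is unrelated to wear experience, there is no shift. The sample-size statement is not shown to be wrong. The analyzable-data text is a secondary clean-up point. Overall this is a worthwhile improvement at almost no cost, not a flaw that undermines the study.

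**What to change.** 1. In Study Time Points, reconcile the two Visit 3 anchors with each other, with the windows and with the wear period in Study Overview. State how a repeated Visit 2 moves the Visit 3 window.
2. For data purposes, replace the late-visit dismissal rule with: subjects seen outside the window still complete the surveys; their data are reported with the actual day of the visit; the event is logged as a deviation.
3. In Statistical Analysis, state that all available survey data are summarised, that dismissals are counted by reason, and that a simple summary without out-of-window subjects is shown alongside.
4. Keep any decision on continued lens wear separate from whether the survey is collected and reported.
5. Remove the analyzable-data text or tie it to a listed procedure, settle *may* against *will*, and state that it is not a ground for omitting survey data.

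The cost is a wording amendment and one extra summary. The downside is slightly more spread in visit day, which the recorded day and the extra summary make visible.
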